11.10 Appendix 10: Cardiac Monitoring

11.10.1 Management of Troponin and Other Cardiac Enzymes Elevation

Subjects with risk factors for, or evidence of, existing heart disease should be closely monitored throughout their treatment with AMG 176. Subjects should be clinically monitored with local and central cardiac monitoring tests for elevated troponin and cardiac enzymes diagnostic of cardiac injury. Local troponin testing will be performed to guide immediate clinical care. Local assessment should include troponin (I or T), CK-MB, and NT-pro-BNP. Serum samples are collected for centralized assessment. Central testing of troponin-I with ADVIA Centaur XP TnI assay will be performed for all screening, grading, and withholding decisions.

Grading of Troponin-I Elevation:

Central testing of cardiac troponin-I will be performed for eligibility determination, grading, and withholding decisions. The following criteria is developed based on CTCAE version 5.0 to determine the grade of troponin-I elevation with ADVIA Centaur XP TnI assay performed by central lab:

- grade 1: isolated elevation of troponin > 99th percentile URL of 0.04 ng/mL for females or 0.059 ng/mL for males
- grade 3: troponin elevation greater than or equal to manufacturer's defined cut-off for MI of 0.78 ng/mL

11.10.2 Management of Cardiac Arrhythmia

Subjects with risk factors for, or evidence of, existing heart disease should be closely monitored throughout their treatment with AMG 176. Subjects should be clinically monitored on ongoing basis for cardiac function (blood pressure, heart rate, ECHO and ECG) according to the Schedule of Activities (Section 1.3). The administration of AMG 176 should be withheld if grade 3 or 4 arrhythmias (including tachycardia) develop or appear to be exacerbated by AMG 176 treatment. For any grade 3 arrhythmia related to AMG 176 administration, the AMG 176 dose should be reduced. Treatment may be resumed once the signs and symptoms resolve to baseline value or grade 1.

Management should be tailored to the appropriate treatment for the underlying cardiac disorder according to the local SOC and institutional guidelines. For any grade 4 arrhythmia related to AMG 176 administration, AMG 176 should be permanently discontinued.

Protocol Number: 20200392

Date: 28 April 2022 Page 141 of 149

11.11 Appendix 11: ECOG Performance Status and NYHA Classification 11.11.1 Eastern Cooperative Oncology Group (ECOG) Performance Status

| 0 | Fully active, able to carry on all predisease performance without restriction |
|---|--|
| 1 | Restricted in physically strenuous activity, but ambulatory and able to carry out work of a light or sedentary nature (eg, light housework, office work) |
| 2 | Ambulatory and capable of all selfcare, but unable to carry out any work activities. Up and about more than 50% of waking hours |
| 3 | Capable of only limited selfcare, confined to bed or chair more than 50% of waking hours |
| 4 | Completely disabled. Cannot carry out any selfcare. Totally confined to bed or chair |
| 5 | Dead |

ECOG = Eastern Cooperative Oncology Group; NYHA = New York Heart Association.

11.11.2 New York Heart Association Functional Classification

| | _ |
|-----------|---|
| Class I | No limitation of physical activity. Ordinary physical activity does not cause undue fatigue, palpitation or dyspnea. |
| Class II | Slight limitation of physical activity. Comfortable at rest, but ordinary physical activity results in fatigue, palpitation or dyspnea. |
| Class III | Marked limitation of physical activity. Comfortable at rest, but less than ordinary activity causes fatigue, palpitation or dyspnea. |
| Class IV | Unable to carry out any physical activity without discomfort. Symptoms of cardiac insufficiency may be present even at rest. If any physical activity is undertaken, discomfort is increased. |

Protocol Number: 20200392

Date: 28 April 2022 Page 142 of 149

11.12 Appendix 12. Uniform Response Criteria for Myelodysplastic/ Myeloproliferative Neoplasms (MDS/MPN)

CR (presence of all of the following improvements)^a

Bone marrow: $\leq 5\%$ myeloblasts (including monocytic blast equivalent in case of CMML) with normal maturation of all cell lines and return to normal cellularity^a

- Osteomyelofibrosis absent or equal to "mild reticulin fibrosis" (≤ grade 1 fibrosis)^b
 - Peripheral blood^c
 - WBC ≤ 10 x 10⁹ cells/L
 - Hgb ≥ 11 g/dL
 - Platelets $\geq 100 \text{ x } 10^9/\text{L}; \leq 450 \text{ x } 10^9/\text{L}$
 - Neutrophils ≥ 1.0 x 10⁹/L
 - Blasts 0%
 - Neutrophil precursors reduced to ≤ 2%
 - Monocytes ≤ 1 x 10⁹/L

Extramedullary disease: Complete resolution of extramedullary disease present before therapy (eg, cutaneous disease, disease-related serous effusions), including palpable hepatosplenomegaly

Provisional category of CR with resolution of symptoms^c: CR as described above, and complete resolution of disease-related symptoms as noted by the MPN Symptoms Assessment Form (MPN-SAF) Total Symptom Score (TSS)

Persistent low-level dysplasia is permitted given subjectivity of assignment of dysplasia^a

Complete Cytogenetic Remission

Resolution of previously present chromosomal abnormality (known to be associated with myelodysplastic syndrome, myeloproliferative neoplasms, or MDS/MPN), as seen on classic karyotyping with minimal of 20 metaphases or FISH^d

Protocol Number: 20200392

Date: 28 April 2022 Page 143 of 149

Partial Remission

Normalization of peripheral counts and hepatosplenomegaly with bone marrow blasts (and blast equivalents) reduced by 50%, but remaining > 5% of cellularity except in cases of MDS/MPN with $\le 5\%$ bone marrow blasts at baseline

Marrow Response

Optimal marrow response: Presence of all marrow criteria necessary for CR without normalization of peripheral blood indices as presented above

Partial marrow response: Bone marrow blasts (and blast equivalents) reduced by 50%, but remaining > 5% of cellularity, *or* reduction in grading of reticulin fibrosis from baseline on at least 2 bone marrow evaluations spaced at least 2 months apart

Clinical Benefit

Requires 1 of the following in the absence of progression or CR/partial response and independent of marrow response (cord blood response must be verified at \geq 8 weeks) to be considered a clinical benefit

Erythroid Response

- Hemoglobin (Hgb) increase by ≥ 2.0 g/dL
- Transfusion independence (TI) for ≥ 8 weeks for patients requiring at least 4 packed red blood cell transfusions in the previous 8 weeks
- Only red blood cell transfusions given based on physician's judgment for a pretreatment Hgb of ≤ 8.5 g/dL will count in the red blood cell TI response evaluation^e

Platelet Response

- Transfusion independence when previously requiring platelet transfusions of at least a rate of 4 platelet transfusions in the previous 8 weeks
- Pretreatment \leq 20 x 10 9 /L: increase from < 20 x 10 9 /L to > 20 x 10 9 /L and by at least 100 9 /.
- Pretreatment > 20 x 10⁹/L but ≤ 100 x 10⁹/L: absolute increase of ≥ 30 x 10⁹/L^e

Neutrophil Response

- Pretreatment ≤ 0.5×10^9 /L at least 100% increase and an absolute increase ≥ 0.5×10^9 /L
- Pretreatment > 0.5 x 10^9 /L and ≤ 1.0 x 10^9 /L at least 50% increase and an absolute increase ≥ 0.5 x 10^9 /Le
- Spleen Response

Protocol Number: 20200392

Date: 28 April 2022 Page 144 of 149

 Either a minimum 50% reduction in palpable splenomegaly of a spleen that is at least 10 cm at baseline or a spleen that is palpable at more than 5 cm at baseline becomes not palpable

- Symptom Response
 - Improvement in symptoms as noted by decrease of ≥ 50% as per the MPN-SAF TSS scoring < 20 were not considered eligible for measuring clinical benefit^f

Progression

Requires at least one of the following in the absence of another explanation (eg, infection, bleeding, ongoing chemotherapy, etc.):

- \geq 50% reduction from maximum response levels in granulocytes or platelets
- Reduction in hemoglobin by ≥ 1.5 g/dL

Transfusion dependence

Relapse

Requires at least one of the following:

- Return to pre-treatment bone marrow blast percentage
- Decrease of ≥ 50% from maximum response levels in granulocytes or platelets
- Transfusion dependence or hemoglobin level ≥ 1.5 g/dL lower than prior to therapy
- CMML = chronic myelomonocytic leukemia; CR = complete response; FISH = fluorescence in situ hybridization; Hgb = hemoglobin; IWG = International Working Group; MDS = myelodysplastic syndrome; MPN = myeloproliferative neoplasm; MPN-SAF = MPN Symptoms Assessment Form; TI = transfusion independence; TSS = Total Symptom Score; WBC = white blood cells
- ^aPresence of dysplastic changes, which may be interpreted within the scope of normal range of dysplastic changes, may still exist in the presence of CR as allowed in MDS IWG. Marrow should exhibit age-adjusted normocellularity in CR.
- ^bIf there is no significant fibrosis present on the initial bone marrow biopsy, a second biopsy is not required to prove resolution of fibrosis. Grading of fibrosis in measurement of treatment response should be according to the European Consensus System.
- ^cGiven the current lack of a validated tool to assess complete resolution of symptoms in MDS/MPN, "CR with resolution of symptoms" (a complete resolution of disease-related symptoms as noted by the MPN-SAF TSS in presence of CR) will be a provisional category of disease response.
- dLoss of cytogenetic burden of disease by (via FISH or classic karyotyping) known to adversely affect prognosis is required to reach complete cytogenetic remission. Decrease in the cytogenetic burden of disease must be by ≥ 50% (via FISH or classic karyotyping) to be indicative of a partial cytogenetic response. Given variability of fluorescent probes used in FISH, cytogenetic normalization via FISH will depend on the performance characteristics of the specific probes used.

Protocol Number: 20200392

Date: 28 April 2022 Page 145 of 149

eResolution of abnormal peripheral blood counts must persist for at least 2 separate analyses over at least 8 weeks. In the case of proliferative MDS/MPN, CR will include resolution of thrombocytosis to a normal platelet count (150 to 450 x 10^9 /L) and resolution of leukocytosis to WBC ≤ 10×10^9 cells/L but ≥ 1.5×10^9 /L. Hemoglobin should be maintained > 11 g/dL and platelets ≥ 100×10^9 /L without the support of transfusions. Clinical benefit may occur when these changes occur in absence of other changes required for CR or marrow response. Platelet and packed red blood cell TI would be considered for clinical benefit, and duration of TI should be monitored. Reduction in myeloid precursors (promyelocytes, myelocytes, metamyelocytes, nucleated red blood cells) to less than appreciable levels (≤ 2×10^9) and/or 1×10^9 /L monocytosis in the absence of infection, cytokine treatment, or other reactive causes. MPN-SAF TSS validation among patients with MDS/MPN is currently under way (Mesa, 2014).

Protocol Number: 20200392

Date: 28 April 2022 Page 146 of 149

11.13 Appendix 13. Medications That may Cause QTc Prolongation

List of medications known to cause corrected QT interval (QTc) interval prolongation is available at the following link: http://www.azcert.org/medical-pros/drug-lists/drug-lists.cfm

If participant in this study does not have access to the internet, they can contact the institution investigational pharmacy or contact their study physician to obtain a list.

The following table presents a list of drugs that may prolong the QTc. This is not an inclusive list of drugs and is provided for guidance only. The participant is encouraged to follow the list in this link above for the most up-to-date information. These drugs are prohibited during the study with the exception of ciprofloxacin for use in neutropenic subjects with acute myeloid leukemia. Washout period is based on roughly 5 half-lives and rounded to a convenient interval. This list includes (but is not limited to) the following:

| Compounds | Compound Half-life | Possible Washout Period – Hours | Possible Washout Period - Days |
|----------------------------|---|---------------------------------------|--------------------------------------|
| Alfuzosin | ~ 10 hours | | 7 |
| Amantadine | 17 \pm 4 hours (10-25) | | 4 |
| Amiodarone (cordarone) | 58 days (15 142) 36 days (active metabolite) | | 180 |
| Amitriptyline ^a | > 24 hours, wide interpatient variability | | |
| Arsenic trioxide | Not characterized | | |
| Azithromycin | 40 hours | | |
| Bepridil | 42 hours (26 to 64) | | 10 |
| Chloral hydrate | Readily converted to Trichloroethanol (active metabolite $t_{1/2} = 7$ to 10 hours) | 48 | |
| Chloroquine | Prolonged (days to weeks) | | |
| Chlorpromazine | 30 ± 7 hours | | |
| Clarithromycin | Non-linear PK3 to 4 hr (250 mg Q12) 5 to 7 hr (500 mg Q12) | 36 | |
| Chloroquine | 6 to 60 days; mean 20 days | | |
| Desipraminea | > 24 hours, wide interpatient variability | | |
| Disopyramide | 6.7 hr (4 to 10) | 36 | |
| Dofetilide | 10 hours | 48 | |
| Dolasetron | 8.1 hours | | |
| Domperidone | 7 to 8 hours | 48 | |
| Doxepina | > 24 hours, wide interpatient variability | | |
| Droperidol | 2.2 hours | 10 | |

Page 1 of 3

Footnotes defined on the last page of the table.

Protocol Number: 20200392

Date: 28 April 2022 Page 147 of 149

| Compounds | Compound Half-life | Possible Washout Period – Hours | Possible Washout Period - Days |
|-----------------------------|---|------------------------------------|-----------------------------------|
| Erythromycin | Each salt form has different Half-Life ^a | | |
| Felbamate | 20 to 23 hours | | 5 |
| Flecainide | 20 hours (12 to 27) | | 5 |
| Foscarnet | 87.5 ± 41.8 hours distribution and release from bone ^a | | 20 |
| Fosphenytoin | 12 to 29 hours | | 6 |
| Gatifloxacin | 7 to 14 hours | 48 | |
| Gemifloxacin | 7 hours | 48 | |
| Grepafloxacin | 16 hours | | 3 |
| Halofantrine | 6 to 10 days (variable among individual) | | 45 |
| Haloperidol | 18 ± 5 hours | | 5 |
| Ibutilide | 6 hours (2 to 12) variable among subject ^a | 36 | |
| Imipramine* | > 24 hours, wide interpatient variability | | |
| Indapamide | 14 hours (biphasic elimination) | | 3 |
| Isradipine | 8 hours (multiple metabolites) | 48 | |
| Levofloxacin | 6 to 8 hours | 48 | |
| Levomethadyl | Multiple compartment PK with active metabolite 2.6 days for LAAM, 2 day for | | 20 |
| | nor-LAAM, 4 day for dinor-LAAM | | _ |
| Lithium | 24 hours (10 to 50) | | 7 |
| Mesoridazine | 24 to 48 hours (animal study) | | 10 |
| Methadone Moexipril/HCTZ | 15 to 30 hours 2 to 9 hours (include active metabolite) for moexipril; 5.6 to 14.8 hours for HCTZ | 48 | 7 |
| Moxifloxacin | 12 ± 1.3 hours | 72 | |
| Naratriptan | 6 hours | 36 | |
| Nicardipine | ~ 2 hour post IV infusion | 12 | |
| Nortriptyline ^a | > 24 hours, wide interpatient variability | | |
| Octreotide | 1.7 hours | 12 | |
| Ofloxacin | 5 to 7.5 hours | | 2 |
| Ondansetron | 4 hours (IV/IM); 3 hours (PO) | | 1 to 3 |
| Pentamidine | 6.4 ± 1.3 hours | 36 | |
| Pimozide | 55 hours | | 10 |
| Procainamide | 3 to 4 hours for PA and NAPA (active metabolite) | 24 | |
| Protriptyline ^a | > 24 hours, wide interpatient variability | | |

Page 2 of 3

Footnotes defined on the last page of the table.

Protocol Number: 20200392

Date: 28 April 2022 Page 148 of 149

| Compounds | Compound Half-life | Possible Washout Period – Hours | Possible Washout Period - Days |
|---------------|---|------------------------------------|-----------------------------------|
| Quetiapine | 6 hours | 36 | |
| Quinidine | 6 to 8 hours in adult; 3 to 4 hours in children | 36 | |
| Quinine | 4 to 5 hours | | |
| Risperidone | 3 to 20 hours (extensive to poor metabolizer) | | 4 |
| | 9-hydroxyrisperidone (active metabolite) $t_{1/2}$ = 21 to 30 hours (extensive to poor metabolizer) | | |
| Salmeterol | 5.5 hours (only one datum) | 36 | |
| Sotalol | 12 hours | 72 | |
| Sparfloxacin | 20 hours (16 to 30) | | 4 |
| Sumatriptan | 2.5 hours | 12 | |
| Tacrolimus | ~ 34 hours in healthy; ~19 hours in Kidney transplant | | 7 |
| Tamoxifen | 5 to 7 days (biphasic) | | 30 |
| Telithromycin | 2 to 3 hours | 24 | |
| Thioridazine | 20 to 40 hours (Phenothiazines) | | 7 |
| Tizanidine | 2.5 hours | 12 | |
| Vardenafil | 4 to 5 hours | | |
| Venlafaxine | 5 ± 2 hours for parent comp. 11 ±2 hours for OVD (active metabolite) | 60 | |
| Voriconazole | 6 hours; dose dependent | | |
| Ziprasidone | 7 hours | 36 | |
| Zolmitriptan | 2.8 to 3.7 hours (higher in female) | 18 | |

Page 3 of 3

References:

Physician's Desk Reference 2002

Facts and Comparison (update to June 2005)

The Pharmacological Basis of Therapeutics 9th Edition, 1999

HCTZ = hydrochlorothiazide; IV = intravenous; IM = intramuscular; LAAM = levo-alpha-acetylmethadol; NAPA = N-acetylprocainamide; OVD = O-desmethylvenlafaxine; PA = procainamide; PK = pharmacokinetics; PO = once daily; Q12 = every 12 hours; QT = QT interval; t_{1/2} = elimination half-life.

^a Weakly associated with Torsades de pointes and/or QT prolongation but that are unlikely to be a risk for Torsades de pointes when used in usual recommended dosages and in subjects without other risk factors (eg, concomitant QT prolonged drugs, bradycardia, electrolyte disturbances, congenital long QT syndrome, concomitant drugs that inhibit metabolism).

Protocol Number: 20200392

Date: 28 April 2022 Page 149 of 149

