4.3.2 Justification for Non-investigational Product Dose

The dose of azacitidine for the first treatment cycle, for all subjects regardless of baseline hematology laboratory values, is 75 mg/m² subcutaneously or intravenously, daily for the first 7 days of a 4-week cycle (as per local prescribing information). Prophylactic treatment to mitigate nausea and vomiting will be administered.

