5.1 Inclusion Criteria

Subjects are eligible to be included in the study only if all of the following criteria apply:

- 101 Age \geq 18 years of age.
- Eastern Cooperative Oncology Group (ECOG) performance status of 0 to 2. Refer to Section 11.11.1 for more details.
- For Part 1, patients have R/R MDS post-HMA failure, defined as prior receipt of 4 cycles of HMA therapy (including but not limited to decitabine, azacitidine, investigational HMAs such as SGI-110, and oral HMAs such as ASTX727 and CC-486) with failure to attain a response or progression of disease or relapse at any time after prior response to HMA therapy.

Note:

Protocol Number: 20200392

Date: 28 April 2022 Page 45 of 149

1) Patients with HR-CMML (CMML, CMML-1 or 2 by World Health Organization [WHO]) are eligible.

- 2) Hydroxyurea administration will be allowed on the study to lower the white cell count to $\leq 10\,000/\mu L$ prior to the initiation of therapy.
- 104 For Part 2, patients will be divided into 2 cohorts:
 - a. HMA Failure Cohort: patients with R/R MDS post-HMA failure (defined as prior receipt of 4 cycles of HMA therapy with failure to attain a response or progression of disease or relapse at any time after prior response to HMA therapy) are eligible. Patients who have previously received venetoclax are eligible and will be stratified accordingly in the HMA Failure Cohort.
 - **b.** Newly Diagnosed Cohort: patients with treatment-naïve newly diagnosed HR-MDS (IPSS score ≥ 3.5) are eligible.

Note

- 1) Patients with HR-CMML (CMML-1 or 2 by WHO) are eligible.
- 2) Hydroxyurea administration will be allowed on the study to lower the white cell count to $\leq 10\,000/\mu L$ prior to the initiation of therapy.
- 3) Patients who have previously received venetoclax are eligible and will be stratified accordingly in the HMA Failure Cohort.
- 105 Must be willing and able to undergo bone marrow aspirate at screening.
- Life expectancy of > 3 months, in the opinion of the investigator.
- Hepatic function, as follows: AST, and Alanine Aminotransferase (ALT) < 3 X ULN, total bilirubin < 1.5 X ULN (except subjects with Gilbert's syndrome).
- 108 Cardiac function, as follows; Left Ventricular Ejection Fraction (LVEF) > 50% 2D transthoracic ECHO is the preferred method of evaluation. Multigated Acquisition (MUGA) scan is acceptable if ECHO is not available.

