 - Positive Hepatitis C Virus Antibody (HCVAb): hepatitis C virus RNA by PCR is necessary. Detectable hepatitis C virus RNA suggests chronic hepatitis C. Negative for PCR test can be enrolled in the study.

Prior/Concomitant Therapy

- 211 Treatment with medications known to cause corrected QT Interval (QTc) interval prolongation within 1 week prior to enrollment unless approved by the Amgen Medical Team.
- Anti-tumor therapy: chemotherapy within 14 days (or 5 half-lives, whichever is shorter) of enrollment, antibody therapy, molecular targeted therapy, or investigational agent within 21 days (or 5 half-lives, whichever is shorter) of

Protocol Number: 20200392

Date: 28 April 2022 Page 47 of 149

enrollment. Exceptions: hydroxyurea to control peripheral blood leukemic cell counts is allowed until prior to receiving the first dose of AMG 176.

- 213 Prior systemic radiation therapy must have been completed at least 28 days prior to enrollment. Prior focal radiotherapy completed at least 14 days prior to enrollment.
- Patient has received a live attenuated vaccine within 4 weeks prior to the first dose of study drug. Patients who have received coronavirus disease 2019 (COVID-19) vaccine within **14** days prior to dosing, or plan to receive a COVID-19 vaccine within 28 days postdose; from 29 days postdose through EOS, vaccination for COVID-19 may be deemed acceptable for a subject following discussion and agreement between the sponsor and the investigator.
- Use of any medications (except anti-tumor medications), including herbal medicines (eg, St. John's wort), vitamins, or supplements consumed by the subject within the 30 days prior to enrollment, and continuing use if applicable, that was not reviewed and approved by the PI and the Amgen Medical Monitor prior to enrollment. Written documentation of this review and Amgen acknowledgment is required for subject participation.
- Use of known strong inhibitors of CYP3A4/P-gp within the 14 days or 5 half-lives (whichever is longer) or products containing grapefruit juice, Seville oranges, or St. John's wort within 7 days, prior to enrollment unless reviewed and approved by the principal investigator and the Amgen medical monitor prior to enrollment. Written documentation of this review and Amgen acknowledgment is required for subject participation.

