6.1.7 Excluded Treatments, Medical Devices, and/or Procedures During Study Period

The following medications and/or therapies should not be administered within the timeframes specified prior to enrollment or during the study (unless otherwise specified below):

- Allogenic stem cell transplant.
- Autologous stem cell transplant.
- Anti-tumor therapy (chemotherapy, antibody therapy, molecular targeted therapy, retinoid therapy, or investigational agent or procedures); concurrent use of bisphosphonates or denosumab for bone loss are permitted.
- Treatment with medications known to cause QTc interval prolongation unless approved by the Amgen Medical Team.
- Any live vaccine therapies used for the prevention of infectious disease.
- Any major surgery or radiotherapy unless agreed upon by Amgen and investigator.
- Over the counter medication(s) that was not reviewed and approved by the principal investigator and the Amgen medical monitor.
- Herbal medicines (eg, St. John's wort) that were not reviewed and approved by the principal investigator and the Amgen medical monitor.

The use of certain medications and illicit drugs within 5 half-lives or 28 days, whichever is shorter prior to the first dose of study drug and for the duration of the trial will not be

Protocol Number: 20200392

Date: 28 April 2022 Page 57 of 149

allowed. If a prohibited medication is required for single use (such as for a procedure) while study drug is held, the Amgen medical monitor can approve such use.

The following medications or non-drug therapies are prohibited:

 Use of known strong inhibitors of CYP3A4/P-gp such as ketoconazole, itraconazole, HIV protease inhibitors, nefazodone, cyclosporine, erythromycin, clindamycin, tetracycline, and clarithromycin within the 14 days or 5 half-lives (whichever is longer) or products containing grapefruit, Seville oranges, or St. John's wort within 7 days, prior to enrollment.

- Use of known CYP3A4 sensitive substrates with a narrow therapeutic window (such as pimozide, and sirolimus) within 5 half-lives of the drug or its major active metabolite, whichever is longer, following the last dose of the drug prior to receiving the first dose of AMG 176. Refer to prescribing information for concomitant medications.

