6.2.2.2 AMG 176 Management of Toxicities

6.2.2.2.1 Management of Infections

Subjects with evidence of existing infection should be closely monitored while being treated with AMG 176. Subjects with active systemic infections requiring IV antibiotics, antivirals, or antifungals should not be dosed with AMG 176 until infection has resolved and if being treated with an anti-infectious therapy, the course of such therapy should have been completed. Management should be tailored to the appropriate prophylaxis and/or treatment for the underlying infection according to the local SOC and institutional guidelines with the exception of excluded medications detailed in Section 6.1.7.

Infection Prophylaxis

Subjects who may experience neutropenia are at a high risk for infectious complications. As appropriate, these subjects should be administered prophylactic antibacterial (eg, treatment with ciprofloxacin) and antifungal (treatment with amphotericin B or echinocandins).

Protocol Number: 20200392

Date: 28 April 2022 Page 68 of 149

These subjects should be monitored for early signs of breakthrough infections after the initiation of antibacterial therapy to prompt additional evaluation and possible therapy modification. Subjects experiencing diarrhea should be closely monitored for their electrolyte levels.

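### Appendix 13 bans QT-prolonging drugs with no approval route and exempts ciprofloxacin only in AML, contrary to Sections 6.1.7 and 6.2.2.2.1 (minor)

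*Protocol*

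**What the plan says.** Four parts of the protocol set a rule for QT-prolonging drugs or for ciprofloxacin.

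- Appendix 13 (Section 11.13), introducing its drug table: "These drugs are prohibited during the study with the exception of ciprofloxacin for use in neutropenic subjects with acute myeloid leukemia". No approval by the sponsor is mentioned.
- Section 6.1.7, among treatments excluded during the study: "Treatment with medications known to cause QTc interval prolongation unless approved by the Amgen Medical Team". The same section lets the medical monitor approve single use of a prohibited drug while study drug is held.
- Exclusion criterion 211 (Section 5.2) applies the same approval at entry, excluding subjects treated with drugs that cause QTc "interval prolongation within 1 week prior to enrollment unless approved by the Amgen Medical Team".
- Section 6.2.2.2.1, on subjects who may become neutropenic: "these subjects should be administered prophylactic antibacterial (eg, treatment with ciprofloxacin". It sets no AML restriction.

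The population is defined in Section 5.1: "For Part 1, patients have R/R MDS post-HMA failure". Part 2 takes HMA failures and newly diagnosed higher-risk MDS, and CMML-1 or CMML-2 is allowed in both parts.

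On anti-emetics, Section 4.3.2 says of azacitidine treatment: "Prophylactic treatment to mitigate nausea and vomiting will be administered". The Appendix 13 table has rows for both "Ondansetron | 4 hours (IV/IM); 3 hours (PO" and "Dolasetron | 8.1 hours".

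**The concern.** One protocol gives two answers to the same practical question: may a subject on study receive a QT-prolonging drug if the sponsor agrees? Section 6.1.7 says yes and Appendix 13 says no. The single exception in the appendix is written for a disease that the trial does not enrol, so it helps none of the subjects for whom Section 6.2.2.2.1 suggests ciprofloxacin.

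The situation would be common. Section 2.3.2 counts neutropenia, nausea and vomiting among the identified risks of AMG 176, and Section 6.2.2 expects myelosuppression during therapy. A site that followed the appendix to the letter could withhold an antibiotic or anti-emetic that the body of the protocol lets the sponsor approve, or record its use as a deviation. Because QTcF prolongation is a DLT criterion in Table 6-2, the route for permitting these drugs should be clear.

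**Working it through.** No formula applies and the plan states no figure on this point, so the check compares the texts.

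**1. Ciprofloxacin in a neutropenic MDS subject on treatment.**

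| Source | Result for this subject |
|---|---|
| Section 6.2.2.2.1 | Named as example prophylaxis, within the limits of Section 6.1.7 |
| Section 6.1.7 | Allowed with medical team approval |
| Appendix 13 | Prohibited; the exception needs AML, and there is no approval route |

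The first two rows are compatible. The third contradicts both. Ciprofloxacin has no row in the table, but the appendix says its list is not limited to the rows shown, and an exemption for ciprofloxacin makes sense only if the drug is otherwise covered.

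**2. Reach of the AML exemption.** Section 5.1 defines three eligible populations: Part 1 relapsed/refractory, Part 2 HMA failure, and Part 2 newly diagnosed. Each is MDS or CMML, so the exemption covers 0 of 3. These are eligible populations, not groups actually treated: the SAP (Section 3.1) records that Part 2 did not enrol. A subject could transform to AML on study, and time to transformation is a Part 2 secondary endpoint, but nobody enters with AML.

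**3. Listed anti-emetics.** Ondansetron and dolasetron are both in the table without an exemption. Under Appendix 13 each is barred; under Section 6.1.7 each can be approved. The conflict has the same form as in step 1. Section 4.3.2 requires prophylaxis and Section 6.7.2 lists anti-emetics as supportive care, but neither names an agent.

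**4. Which text governs.** Section 6.7.2 limits supportive care by reference to Section 6.1.7, and Section 6.2.2.2.1 does the same for infection management. No section visible in the released protocol cites Appendix 13. The natural reading is that Section 6.1.7 controls and that the appendix sentence is the one in error.

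**5. Effect on the statistics.** No sample size, stopping boundary, operating characteristic or estimate in the protocol or SAP uses the Appendix 13 rule. Nothing numerical changes.

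**The case against.** The best defence is that no careful reader would be misled. The paragraph containing the prohibition calls the list non-exhaustive guidance. The operative sections send the reader to Section 6.1.7, which has an approval route and a single-use route, and its closing text refers doubtful cases to the medical monitor. No document shows a site withholding a drug. SAP Section 9.3 provides no listing of protocol deviations, so an appendix-driven deviation would not appear in a planned output. These points stand, and they keep the matter minor. They do not make the sentence right: it still says prohibited, with one exception that fits no eligible population.

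Three stronger readings are tempting, and the documents support none of them.

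- *A reader might infer that required anti-emetic prophylaxis is impossible under the appendix.* It is not. No agent is named, so an unlisted one satisfies Sections 4.3.2 and 6.7.2, and a listed one can be approved under Section 6.1.7.
- *A reader might infer that criterion 211 is too short*, because the appendix table shows 180 days for amiodarone and 45 for halofantrine against a 1-week entry window. The table columns are headed as possible washout periods within a guidance list; they are not eligibility rules. Section 6.1.7 also caps the exclusion window for certain medications at the shorter of 5 half-lives and 28 days, though it does not make clear which drugs this covers. No QT effect size, co-medication frequency or QTcF event rate is given, so no effect on DLTs is shown.
- *A reader might infer that the SAP conceals co-medication by producing no such output.* SAP Section 9.6.10 states the omission openly, and Section 9.1 explains that reporting is confined to listings. The absence of a matching entry in SAP Section 10 is a documentation matter unrelated to Appendix 13.

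**Conclusion.** The point holds as a minor internal contradiction. Appendix 13 states an absolute rule that Section 6.1.7 and criterion 211 do not share, and an exemption restricted to a disease outside the trial. At least two listed anti-emetics meet the same conflict.

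The conclusion rests on two readings: that the exemption clause brings ciprofloxacin within the ban although it has no table row, and that Section 6.1.7 is the intended rule because the operative sections refer to it. The possible harm is a site-level misreading of supportive care; none is documented. The SAP records early termination, so for this study the wording is largely moot.

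**What to change.** Rewrite the Appendix 13 sentence so that the listed drugs are prohibited on study unless the sponsor's medical team approves them, with a cross-reference to Section 6.1.7, and delete the AML-only ciprofloxacin clause.

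Replacing AML with MDS/CMML in the existing sentence would not be enough. It would exempt ciprofloxacin in the appendix while Section 6.1.7, which has no ciprofloxacin exemption, still required approval. If the clinical team wants ciprofloxacin allowed without case-by-case approval in neutropenic MDS/CMML subjects, that exemption should appear in both places. Whether to allow it is a clinical decision.

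The cost is one sentence in the appendix, plus one in Section 6.1.7 if the exemption is wanted. No new data are collected and no analysis changes. With the study closed, the edit is worth making wherever this appendix is carried into another protocol.
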